7.2. Weight

Observed weight values, change from baseline, Z-scores for weight, and change from baseline in Z-scores for weight will be listed and summarized by visit using descriptive statistics. The change in weight z-scores will also be summarized by subject's serum bicarbonate categories.

MMRM analysis will also be performed for changes from baseline and changes in Z-Scores from baseline.

7.3. Height

Observed height values, change from baseline, Z-scores for height, change from baseline in Z-scores for height, height velocity at 1 year, and height velocity Z-score will be summarized by visit using descriptive statistics. Height, Z-scores for height, height velocity and height velocity Z-scores will be calculated as the mean of the three measurements. The number and percentage of subjects with a height Z-score decrease of >0.5 , >1.0 , and >2.0 will be listed and summarized by visit using descriptive statistics. MMRM analysis will also be performed for changes from baseline and changes in Z-Scores from baseline.

The change in height z-scores will also be summarized by subject's serum bicarbonate categories.

Height velocity values and associated Z-scores will be computed for each post-baseline year in the study, based on the methods described in [Appendix 6](#).

7.4. Bone Mineral Density (BMD) and Bone Mineral Content (BMC)

DEXA measurements will include posterior-anterior spine and total body less head areal (TBLH) BMD and BMC. Observed BMD (spine and TBLH) and BMC (spine and TBLH) values change from baseline, Z-scores as well as height adjusted Z-scores for BMD and BMC, change from baseline in Z-scores and height adjusted Z-scores for BMD and BMC, and percent change from baseline in BMD and BMC will be summarized by visit using descriptive statistics. The number and percentage of subjects with a BMD Z-score and adjusted Z-score decrease of >0.5 , >1.0 , and >2.0 will be listed and summarized by visit using descriptive statistics. MMRM analysis will also be performed for changes from baseline, changes in Z-Scores from baseline, and changes in height adjusted Z-Scores from baseline.

Subjects with a clinically important reduction in BMD defined as change in Z-score and height adjusted Z-score of -0.5 or greater) at 6 months or 12 months, will have a repeat DEXA scan 6 months after discontinuation of study drug. These subjects will be summarized and listed in the DEXA table and listing.

The change in BMD z-scores will also be summarized by subject's serum bicarbonate categories.

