There may be an optional post-study follow-up phase to obtain DEXA measurements in a subgroup of subjects who experience a clinically important reduction (change in Z-score of -0.5 or greater) in BMD, based on local DEXA scan results, after 1 year of treatment with topiramate, to determine whether a decrease in BMD after or during 1 year of treatment with topiramate is reversible. These subjects will have a repeat DEXA scan 6 months after discontinuation of study drug. During study conduct, the sponsor will assess site/investigator interest for participation in this phase to determine if the follow-up phase will be included. An additional consent/assent will be required for this phase.

An external, independent Data Monitoring Committee (DMC) will be commissioned for this study. See Section 11.5, Data Monitoring Committee, for details.

A diagram of the study design is provided in [Figure 1](#).

Figure 1: Study Diagram

^a Optional post-study follow-up phase to obtain DEXA measurements in a subgroup of subjects who experience a clinically important reduction (change in Z-score of -0.5 or greater) in BMD, based on local DEXA scan results, after 1 year of treatment with topiramate; these subjects will have a repeat DEXA scan 6 months after discontinuation of study drug.

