9.1.5. Post-Study Phase (Follow-Up)

There may be an optional post-study follow-up phase to obtain DEXA measurements in a subgroup of subjects who experience a clinically important reduction (change in Z-score of -0.5 or greater) in BMD, based on local DEXA scan results, after 1 year of treatment with topiramate, to determine whether a decrease in BMD after or during 1 year of treatment with topiramate is reversible. These subjects will have a repeat DEXA scan 6 months after discontinuation of study drug.

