11.4. Safety Analyses

The key safety endpoints will include:

- Percentage of subjects with kidney stones
- Change from baseline in weight Z-score over time
- The following height analyses will be conducted for prepubertal subjects (2 to 9 years of age), subjects 10 to 15 years of age, and subjects 2 to 15 years of age:
 - Height at 1 year postbaseline
 - Height change from baseline over time
 - Height Z-score at 1 year postbaseline
 - Change from baseline in height Z-score over time
 - Height velocity at 1 year postbaseline
 - Height velocity Z-score at 1 year postbaseline
 - Percentage of outlier subjects with height Z-score decrease of >0.5 , >1.0 , and >2.0 over time
- The following BMD and BMC endpoints:

- BMD and BMC over time
 - BMD and BMC change from baseline over time
 - Z-score for BMD and BMC over time
 - Change from baseline in Z-score for BMD and BMC over time
 - Percent change from baseline in BMD and BMC over time
 - Percentage of outlier subjects with BMD Z-score decrease of >0.5 , >1.0 , and >2.0 over time
- Change from baseline in biochemical markers of bone mineralization including: serum levels of alkaline phosphatase, calcium, phosphorus, parathyroid hormone (intact), 25-hydroxy-vitamin D, 1,25-dihydroxy vitamin D, and IGF-1
 - Change from baseline in serum and urine laboratory tests, eg, bicarbonate, ammonia, renal function tests, and LFTs
 - Change from baseline in bone age

Z-scores for the DEXA scans will be calculated locally at baseline and at M12 to determine eligibility for the study and the Post-Study Follow-Up phase, and centrally for all statistical analyses. The Z-score calculation will take the DEXA machine and the subject's age, sex, height, and ethnicity into consideration. The reference databases for calculating the Z-scores are provided in the DEXA Manual for this study.

Longitudinal endpoints will be analyzed using a mixed-model repeated measures (MMRM) analysis. The MMRM model will include treatment group, age group, visit, treatment-by-visit interaction, baseline measure, and baseline-by-visit interaction. An unstructured covariance will be used. Other appropriate covariance structures will be explored as needed. Confidence intervals with 95% confidence for the estimated treatment differences will be provided at each time point as appropriate. For proportion endpoints, 95% confidence intervals will be provided for the treatment difference. Each of the endpoints will also be summarized by age group.

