7. SAFETY

The safety variables to be summarized include kidney stones, height, weight, BMD and bone mineral content (BMC), biochemical markers of bone mineralization, bone age XR, seizure counts, cognitive, developmental, and behavioral assessments, treatment-emergent AEs, Columbia-Suicide Severity Rating Scale (C-SSRS), cognitive, developmental and behavioral assessments (COGSTATE computerized battery and NEPSY Language scale; Vineland Adaptive Behavioral Scale, Child Behavior Checklist (CBCL)), clinical laboratory tests (hematology, chemistry, urinalysis, and 24-hour urine collection), vital signs and physical exam. Safety variables are to be tabulated by descriptive statistics (n, mean, median, SD, minimum, and maximum; or n and percent). No formal statistical testing is planned.

For markedly abnormal labs and vital signs, age will be calculated at each visit to determine the criteria. Similarly, Vineland, CBCL and Cogstate will be calculated by age at each visit.

Z-scores for weight and height will be calculated using the SAS programs provided by the Centers for Disease Control (CDC) for the calculation of the 2000 CDC growth charts. Z-scores for the BMD and BMC will be provided by the central DEXA reading center (Bioclinica).

Z-scores for the DEXA scans will be calculated locally at baseline only to determine eligibility for the study, and centrally for all statistical analyses. The Z-score calculation will take the DEXA machine and the subject's age, sex, height, and ethnicity into consideration. The reference databases for calculating the Z-scores are provided in the DEXA Manual for this study (please see the imaging charter of attachment 1 for more details).

Longitudinal endpoints will be analyzed using a mixed-model repeated measures (MMRM) analysis. An MMRM analysis is included as sensitivity analysis to explore longitudinal safety data and will be analyzed in the following order.

1. The model includes treatment group, study center, age group (4 age groups), visit, treatment-by-visit interaction, baseline measure, and baseline-by-visit interaction with the unstructured covariance matrix.
2. If this model experiences convergence issues, then the same model with compound symmetric matrix followed by AR1 will be explored instead of unstructured.

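### SAP 7.4 defines the repeat-DEXA group by a rule that conflicts with the protocol and with two other places in the SAP, so its summary would not describe the children actually scanned

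*SAP*

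**What the plan says.** SAP 7.4 defines the group as "Subjects with a clinically important reduction in BMD defined as change in Z-score and height adjusted Z-score of -0.5 or greater" and continues that these children "at 6 months or 12 months, will have a repeat DEXA scan 6 months after discontinuation of study drug". They are then to be summarised and listed with the DEXA results. No treatment arm is named, and the sentence does not say whether the local or the central read decides.

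The protocol describes something narrower. Section 9.1.5 opens with "There may be an optional post-study follow-up phase to obtain DEXA measurements in a subgroup of subjects" and selects them "based on local DEXA scan results, after 1 year of treatment with topiramate". Section 3.1 repeats the rule, gives the purpose (whether the decrease is reversible) and adds: "An additional consent/assent will be required for this phase". Section 11.4 has Z-scores "calculated locally at baseline and at M12 to determine eligibility for the study and the Post-Study Follow-Up phase", with central Z-scores for all statistical analyses. Section 9.3 (Bone Mineralization) likewise has only the baseline and Month 12 scans read locally.

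The SAP also disagrees with itself. Section 2.2 and Table 1 footnote b both limit the repeat scan to a fall after 1 year on topiramate, and footnote b adds the local read. Section 7, however, states: "Z-scores for the DEXA scans will be calculated locally at baseline only to determine eligibility for the study". Section 2.5 also mentions local reading of baseline scans only.

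**The concern.** The follow-up phase exists to show whether a BMD decrease on topiramate reverses after stopping. Bone mineralization is part of the primary objective. SAP section 1 records that sites stay open until outstanding repeat scans are done, so these data are expected.

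A programmer cannot follow SAP 7.4 together with SAP 2.2 and footnote b. If 7.4 is followed, the group to be summarised and the group that can be scanned differ in both directions:

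- **In the SAP 7.4 group, not due a scan under the protocol:** levetiracetam children with a fall, and topiramate children whose fall is present at Month 6 but not at Month 12.
- **Due a scan under the protocol, possibly outside the SAP 7.4 group:** topiramate children selected on the local Month 12 read whose central Z-score, or height-adjusted Z-score, misses the criterion.

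The table would then mix children with and without a follow-up scan, and could leave out some who were scanned. It would not describe reversibility in the scanned children.

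**Working it through.** **1. The rules side by side**

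| Element | SAP 7.4 | Protocol 3.1, 9.1.5, 9.3, 11.4 | SAP 2.2 / Table 1 footnote b |
|---|---|---|---|
| Arm | not named | topiramate | topiramate |
| Time of fall | Month 6 or Month 12 | after 1 year | after 1 year |
| Read | not named | local | not named / local |
| Criterion | Z-score and height-adjusted Z-score | Z-score | Z-score |
| Status | will have a scan | optional, extra consent | optional |

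Protocol 9.3 does use a fall at 6 or 12 months in any child, but there it prompts the central reader to reassess the scan. SAP 7.4 attaches that trigger to the repeat scan.

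**2. Inputs from the plan**

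Protocol 11.2 gives an SD of 0.4 for annual change in BMD Z-score (0.3 to 0.48 across sex and age groups), 100 completers per arm and 29% dropout. Allocation is 1:1. The sample size reproduces: 100 / (1 - 0.29) = 140.8, so 141 per arm and 282 in total. The stated BMD precision of 0.12 does not (1.96 x 0.4 x sqrt(2/100) = 0.111), but nothing below depends on it. The plan gives no figure for the size of the repeat-scan group.

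**3. Lower bound with no drug effect**

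Let p be the chance that a child meets SAP 7.4, equal in both arms. Let e be the chance that a topiramate child meets both SAP 7.4 and the protocol rule, so e is at most p. The share of the SAP 7.4 group with no scan by design is 1 - e/(2p), which is at least 1/2.

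**4. Month 12 falls alone, SD 0.4**

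Levetiracetam, mean change taken as 0: P(change <= -0.5) = Phi(-0.5/0.4) = Phi(-1.25) = 0.106, or 10.6 per 100 completers. Topiramate with mean shift m: Phi((-0.5 - m)/0.4). At m = -0.25 this is Phi(-0.625) = 0.266, so the levetiracetam share of fallers is 0.106/(0.106 + 0.266) = 28%.

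**5. Month 6 or Month 12**

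This step uses a bivariate normal simulation with 1,000,000 draws per arm. These assumptions are not in the documents:

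- Month 6 SD is 0.7 to 1.0 times the Month 12 SD.
- The correlation between the two visits is 0.5 to 0.7.
- Half of the topiramate shift is present at Month 6.
- Z-score and height-adjusted Z-score correlate 0.9 to 1.0.
- Local and central reads agree.
- Scans are complete.

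Example (no effect, both SDs 0.4, correlation 0.5, the two Z-scores identical): 17.6 per 100 in each arm meet SAP 7.4, and 10.5 per 100 topiramate children also meet the protocol rule. The share is 1 - 10.5/(17.6 + 17.6) = 70%.

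| Topiramate shift at Month 12 | Levetiracetam share, Month 12 falls only, SD 0.4 | Share of SAP 7.4 group with no scan by design, SD 0.4 | Same, all runs with SD 0.3-0.48 |
|---|---|---|---|
| 0 | 50% | 54-70% | 52-70% |
| -0.12 | 38% | 42-60% | 33-61% |
| -0.25 | 28% | 31-49% | 19-53% |
| -0.5 | 17% | 18-33% | 8-39% |

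**6. The other direction**

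With no effect, SD 0.4 and a correlation of 0.9 between the two Z-scores, 10.6 per 100 topiramate completers meet the protocol criterion, but only 7.6 to 8.3 of them are also in the SAP 7.4 group. About 2.3 (10.6 - 8.3) to 3.0 (10.6 - 7.6) per 100 would be due a scan yet fall outside the group, before any difference between local and central reads.

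**The case against.** The strongest reply is that this is one loosely worded sentence. SAP 2.2 and footnote b already carry the protocol's arm and timing. SAP 7.4 is silent on arm; it does not order scans for levetiracetam children. All analyses use central Z-scores, so leaving out the local Month 12 read changes a description, not a calculation. SAP 7.4 also already plans counts of BMD Z-score decreases beyond 0.5, 1.0 and 2.0 by visit.

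Most of that is correct, and it limits the point. It does not remove the conflict: 7.4 is the section that specifies this summary, and it sets a group by arm, time and criterion that the other passages do not.

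A reader might go further and infer that unscanned children would count as not recovered, so that a recovery rate would be understated by a calculable amount. The documents do not support that. Neither defines recovery, a recovery percentage or a denominator for one, and SAP 3 bases continuous summaries on children with a valid measurement. Nor does any text exclude the scans of locally selected children. The SAP 7.4 definition simply does not cover those who miss its criterion.

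The size is also fragile. The Month 6 SD, the correlations and the drug effect are assumptions, and the share is small when the SD is low and the effect large.

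**Conclusion.** The point holds as a conflict in current text. SAP 7.4 states a rule that disagrees with the protocol and with SAP 2.2 and Table 1 footnote b, and SAP 7 omits the local read on which the protocol selects children. As written, the summary is defined on a group that does not match the children who can be scanned.

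Under the plan's own null hypothesis with 1:1 allocation, and with local and central reads agreeing, at least about half of the SAP 7.4 group would have no scan by design. With a real topiramate effect the share falls. Over the scenarios run (SD 0.3 to 0.48, shifts from 0 to -0.5) it lies between 8% and 70%, and the lowest values need an SD of 0.3 with a shift of -0.5. Early withdrawals are not modelled. The textual conflict stands without these figures, and no bias in a recovery percentage is claimed.

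**What to change.** 1. Reconcile SAP 7.4 and SAP 7 with SAP 2.2, Table 1 footnote b and the protocol on who is due a repeat scan: arm, time, read, and whether the height-adjusted Z-score is part of the criterion. This review takes no view on which children should be scanned.
2. Define the repeat-scan table and listing as the children who entered the follow-up phase and had a repeat scan. Show central Z-scores and height-adjusted Z-scores at baseline, Month 12 and follow-up. This works however the eligibility wording is settled, and it respects the optional phase and separate consent.
3. Report separately, by arm, the number of children with a central fall of 0.5 or more at Month 6 or Month 12. The by-visit counts are already planned; only the either-visit count is new.
4. Correct SAP 7 to say that local Z-scores are also read at Month 12, as protocol 9.3 and 11.4 state.

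The cost is SAP wording and one table shell. No new scans are needed.

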7.5. Biochemical Markers of Bone Mineralization

Observed and change from baseline in biochemical markers of bone mineralization (serum levels of alkaline phosphatase, calcium, phosphorus, parathyroid hormone (intact), 25-hydroxy vitamin D, 1,25-dihydroxy vitamin D, and IGF-1) will be listed and summarized by visit using descriptive statistics.

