Only AED monotherapy will be used for both treatment groups. However, subjects will not be discontinued from the study if 1 or more concomitant AEDs are added after initiating treatment with study drug. Data will be collected prior to the use of the concomitant AED(s) for the primary analysis. Data subsequently collected while on the concomitant AED(s) will be analyzed in a secondary analysis for each safety outcome of interest.

PHARMACOKINETIC EVALUATIONS

Blood samples (1 mL per sample) for the determination of plasma topiramate and levetiracetam concentrations will be obtained during clinic visits according to the Time and Events schedule. If possible, blood samples for pharmacokinetic (PK) evaluations should be trough samples (ie, taken immediately before the morning dose) and coincide with samples drawn for clinical laboratory tests. During each PK assessment, the dosing regimen, dose administered, time and date of dose administration, time of sample collection, and concomitant medications will be recorded in the case report form.

Pharmacokinetic parameters will not be estimated. Topiramate and levetiracetam plasma concentration data will be summarized.

SAFETY EVALUATIONS

Safety evaluations will include:

- 12-lead electrocardiogram (screening only)
- Vital signs (including orthostatic vital signs), body weight, and height (all visits except Month 2)
- Neurologic and physical examinations (all visits except Month 2)
- Physical activity evaluation (screening)
- Clinical laboratory tests (screening, Month 1, Month 3, Month 6, Month 9, and Month 12/early withdrawal)
- Pregnancy testing (for girls of childbearing potential; serum at screening only; urine at all other visits)
- 24-hour urine collection (Screening, Month 6, and Month 12/early withdrawal)
- Adverse event monitoring, concomitant medication monitoring (throughout)
- Suicidality, as assessed by the Columbia Suicide Severity Rating Scale (C-SSRS; all visits except screening)
- DEXA scan (baseline, Month 6, and Month 12/early withdrawal)
- Renal ultrasound, biochemical bone markers (screening, Month 6, and Month 12/early withdrawal)
- Bone age, as determined by hand/wrist x-ray (baseline and Month 12/early withdrawal)
- Tanner staging of subjects of age 8 years and above (baseline, Month 6, and Month 12 or early withdrawal)
- Seizure counts recorded by parent/guardian in take-home seizure diary (all visits beginning at baseline)

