7.10. Clinical Laboratory Tests

Figures of the mean change from screening (+/- Standard Error) values in continuous hematology, urinalysis and serum chemistry laboratory parameters will be presented by visit. The observed and change from baseline values of lab parameters will also be summarized by visit. For calculation, the signs “<” or “>” will be removed and resulting numerical value will be used. The reference ranges for labs from the SAP will be used, not the reference ranges provided from the Covance.

The shift table of pre- vs. post-treatment with classes for below, within, and above normal ranges will be presented.

The number and percentage of subjects with markedly abnormal (low, high) laboratory hematology, urinalysis/24-hour urine and serum chemistry parameters during the study (from treatment start to 30 days after last dose or the end of treatment visit date, whichever is later) that were not present at baseline will be provided. [Appendix 2](#) presents the markedly abnormal criteria. The conversion factors for 25 Vitamin D, 1, 25 Vitamin D and PTH are also listed.

The laboratory data will be listed. The subjects with any laboratory results outside the reference ranges and the subjects with any markedly abnormal laboratory results will be listed.

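### Bicarbonate and the bone markers are protocol key safety endpoints, but SAP 7.5 and 7.10 do not say that the section 7 MMRM applies to them

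*SAP*

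**What the plan says.** **Protocol.** Section 11.4 lists two relevant items under key safety endpoints: "Change from baseline in biochemical markers of bone mineralization including: serum levels of alkaline phosphatase, calcium, phosphorus" (with PTH, both vitamin D forms and IGF-1), and "Change from baseline in serum and urine laboratory tests, eg, bicarbonate, ammonia, renal function tests, and LFTs". It then says "Longitudinal endpoints will be analyzed using a mixed-model repeated measures (MMRM) analysis", without excluding any endpoint. The model includes treatment, age group, visit, "treatment-by-visit interaction, baseline measure, and baseline-by-visit interaction". On output it says "Confidence intervals with 95% confidence for the estimated treatment differences will be provided at each time point as appropriate". A later paragraph of 11.4, on clinical laboratory tests, asks for descriptive statistics on each analyte by time point, pre/post cross-tabulations against normal ranges, and listings.

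Both groups of endpoints are measured repeatedly. The synopsis schedules "Clinical laboratory tests (screening, Month 1, Month 3, Month 6, Month 9, and Month 12/early withdrawal", so bicarbonate has five post-baseline visits. The bone markers have two, at Months 6 and 12.

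**SAP.** The opening of section 7 repeats the general MMRM sentence, makes the model a sensitivity analysis, sets out a fallback order and promises a 95% CI for treatment differences. It gives no list of endpoints. Sections 7.2, 7.3 and 7.4 each add that an MMRM will also be done, and name the variables. Section 7.5 says of the bone markers only "1,25-dihydroxy vitamin D, and IGF-1) will be listed and summarized by visit using descriptive statistics". Section 7.10 says "The observed and change from baseline values of lab parameters will also be summarized by visit", and adds mean-change figures, shift tables, counts of newly markedly abnormal values, and listings. Neither 7.5 nor 7.10 mentions a model or a treatment difference.

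**The concern.** The protocol's rationale (section 1.2) puts specific emphasis on topiramate-related metabolic acidosis and its links to kidney stones, bone density and growth. Bicarbonate is the first step in that chain, and the bone markers sit between acidosis and bone.

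If the MMRM is run only where an endpoint section calls for it, growth and bone density get an adjusted contrast with an interval, while the proposed mechanism gets by-visit means from whoever attended. The planning assumption is 29% dropout at one year, so visit-wise means and a likelihood-based repeated-measures estimate may differ.

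Age is a second reason to want the adjusted estimate. In SAP Appendix 2 the upper markedly abnormal limit for IGF-1 runs from 50 nmol/L at ages 2-8 to 140 nmol/L at ages 13-16.

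The bicarbonate categories used in 7.2 to 7.4 do not fill the gap. SAP 5.1 defines them at screening as below 20 mEq/L or not, and exclusion criterion 18 bars subjects below 20. The low group should therefore be almost empty, and it says nothing about acidosis on treatment.

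**Working it through.** **1. Which rule reaches which endpoint**

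| Endpoint | Protocol 11.4 general MMRM rule | SAP 7 opening (MMRM as sensitivity) | Endpoint's own SAP section |
|---|---|---|---|
| Weight | yes | yes | 7.2: MMRM stated |
| Height | yes | yes | 7.3: MMRM stated |
| BMD/BMC | yes | yes | 7.4: MMRM stated |
| Bone markers | yes, 2 post-baseline visits | yes, if read literally | 7.5: descriptive only |
| Bicarbonate | yes, 5 post-baseline visits | yes, if read literally | 7.10: descriptive, shifts, abnormal counts |

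If the opening of section 7 were meant to assign the model to every longitudinal endpoint, the sentences in 7.2 to 7.4 would be unnecessary. Their presence there and absence from 7.5 and 7.10 suggests that the latter get no model. The text does not settle it.

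**2. Plan figures**

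No SD, correlation, precision or power is given for bicarbonate or any bone marker, so there is no endpoint-specific figure to reproduce. The planned size does reproduce: 100 completers per arm with 29% dropout gives 100/0.71 = 140.8, so 141 per arm and 282 in total. The 100 per arm is used below for scale only, because enrollment was stopped early (SAP section 1).

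**3. What baseline adjustment is worth (illustration)**

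Assume equal variance σ² at baseline and follow-up, and correlation ρ, the same in both arms.

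- Raw change: variance 2σ²(1−ρ).
- Baseline-adjusted: residual variance σ²(1−ρ²).
- Variance ratio: (1−ρ²)/[2(1−ρ)] = (1+ρ)/2.
- CI width ratio: √[(1+ρ)/2].
- Half-width in SD units with 100 per arm: 1.96·√[2(1−ρ)]·√(2/100) for raw change, and 1.96·√(1−ρ²)·√(2/100) when adjusted.

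| ρ (assumed) | Variance ratio | Width ratio | Narrower by | Raw half-width | Adjusted half-width |
|---|---|---|---|---|---|
| 0.3 | 0.65 | 0.81 | 19% | 0.328 | 0.264 |
| 0.5 | 0.75 | 0.87 | 13% | 0.277 | 0.240 |
| 0.7 | 0.85 | 0.92 | 8% | 0.215 | 0.198 |
| 0.9 | 0.95 | 0.97 | 3% | 0.124 | 0.121 |

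The width ratio does not depend on sample size.

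**4. What the example code returns**

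The model in SAP section 7 contains the treatment-by-visit term, but the least-squares means statement asks for treatment only. That gives one contrast averaged over visits, not a difference at each visit.

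**The case against.** The strongest reply is that the SAP already covers these endpoints. The opening of section 7 is unrestricted, bicarbonate and the bone markers are plainly longitudinal, and a 95% CI is promised. A reader might infer from 7.5 and 7.10 that the SAP withdrew the model from these endpoints and left them with no treatment difference at all. The documents do not support that: nothing says so, and the general rule still stands. What remains is an unresolved scope, with the endpoint sections pointing away from the model.

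Secondly, the protocol's own laboratory paragraph is descriptive, and 7.10 carries it out. Since Protocol 9.3 lists the vitamin D forms, PTH and IGF-1 in the serum chemistry panel, that paragraph arguably reaches the bone markers too. The intervals are also only as appropriate, and Protocol section 11 leaves details to the SAP. This weakens any charge of a clear departure. It does not remove the point, because descriptive summaries and a model are compatible and the same section names these as key endpoints.

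Thirdly, the output is more than raw mean change. Section 7.10 has shift tables and markedly abnormal counts, with bicarbonate limits in Appendix 2. Section 7.9 summarizes metabolic acidosis as an adverse event of special interest. SAP 3.4 adds summaries in four age bands, and the IGF-1 limits are already age-specific. So it would be wrong to say that age is ignored or that only raw change is shown. None of this, however, gives an age- and baseline-adjusted difference with an interval.

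Finally, the MMRM is a sensitivity analysis for every endpoint in this SAP, so its lower status is not peculiar to the laboratory endpoints.

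**Conclusion.** The point holds as a gap in specification. Protocol 11.4 names these as key safety endpoints and has a baseline- and age-adjusted model for longitudinal data. The SAP keeps that model in general terms but applies it by name only in 7.2 to 7.4. An analyst working section by section would produce no adjusted difference or CI for bicarbonate or the bone markers.

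The main loss is the missing estimate and interval. The gain in precision over a raw-change interval is secondary: about 19% to 3% narrower over assumed correlations of 0.3 to 0.9, with equal variances, and small if the correlation is high. A reader might want to turn this into a gain in power. The documents give no basis for that: the SAP plans no formal testing, the trial was sized on CI precision, and no power or correlation is stated for any marker.

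This is a cheap improvement.

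**What to change.** In SAP 7.5, and in 7.10 at least for bicarbonate, add a sentence saying that the section 7 MMRM will also be run on change from baseline, with treatment differences and 95% CIs reported by visit. If the omission is deliberate, record it instead as a change from Protocol 11.4, with the reason.

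Change the least-squares means request in the example code from treatment alone to treatment by visit (`trt*visit`), with the between-arm differences at each visit.

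Use a log transformation only for markers whose data are skewed; the documents do not describe their distributions.

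The cost is a few more tables and a small code change. The necessary data are already collected and the model is already written.
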